Data analysis	
All data analyses will be performed by Dendrite Clinical Systems together with Nordic after the Key Data are completed. Analysed data will be reviewed by an Independent Data Safety Monitoring Committee, involving at least four (4) national coordinating investigators.
 
The analysis of data from the Registry will be descriptive, and all information will be reported in summary tables. Summary data will be provided for all variables collected and the data will be reported overall, by country, and if required by centre. The intention is to focus on those variables most pertinent to assessing compliance with approved labelling and instructions for appropriate use, including use of heparin and monitoring of anticoagulation. The data will also be reviewed for any safety signals. The outcomes to be included in each report will include at least: death, myocardial infarction, renal failure with and without aminoglycoside use, stroke and other embolic or thrombotic event, blood loss (requiring transfusion, requiring re-operation), blood product transfusion and anaphylaxis.
 
Analysis of each outcome will be presented by: country, age categories, sex, presence of anti-platelet agents active at time of operation, cardiac by-pass and operative type. Other variables may be included as considered appropriate by an Independent Data Safety Monitoring Committee or as requested by the PRAC.
 
Overall reports will be synchronised with PSUR scheme and timelines.

Planned milestones	
Study start: planned for Q2 2015
 
Recruitment completed: when a maximum of 5,268 patients will be included (estimated in January 2020). This number of patients should be enough to obtain 3,951 analysable patients.
 
Interim statistical reports: every 6 months after launch.
 
Interim medical report: every 2 years with PSUR.
 
Last data collection: when a maximum of 5,268 patients will be included (estimated in January 2020). This number of patients should be enough to obtain 3,951 analysable patients.
 
Final study report: 12 months after the end of Data collection (prospective collection). The Registry will operate for at least three years beginning with Nordic Aprotinin's return to the market in Europe, and the decision to terminate the Registry will be taken based on agreement with the PRAC.

5. Amendments and updates

Number	Date	Section of the study protocol	Amendment or update	Reason
Version 1.0			submitted 17 September 2014	

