
during the study period
	
...
 
The final study report (data collected prospectively only) will be submitted within 6 months following the completion of the study. If this is delayed for any reason the reasons for the delay will be communicated. The planned publication will conform to STROBE guidelines (cf. References).
	
...
 
The final study report (data collected prospectively only) will be submitted within 12 months following the completion of the study. If this is delayed for any reason the reasons for the delay will be communicated. The planned publication will conform to STROBE guidelines (cf. References).
	
--------------------------------	---	--	--

6. Milestones

Table with planned dates for the following milestones:

Milestone	Planned date	Rationale
Start of data collection	February 2016	At the launch of Nordic Aprotinin in the first participating country (i.e. Aprotinin 10,000 KIU/ml Injection BP in the UK)
End of data collection	when a maximum of 5,268 patients will be included (estimated in January 2020).	This number of patients should be enough to obtain 3,951 analysable patients.
Study progress reports and Interim reports of study results 1	17 May 2018 (with PSUR report)	Clinical study report are done following the same timelines and scheme as PSUR. Bi-annual statistical reports are done for DSMC review
Study progress reports and Interim reports of study results 2	28 May 2020 (with PSUR report)	
Registration in the EU PAS register	8 February 2019	Last update
Final report of study results	Estimated December 2020	The final report of study results (data collected prospectively only) will be made available twelve months after the last patient included

7. Rationale and background

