9.3.7. Post-operative*

Reoperation if required with reason for re-operation;

The occurrence of post-operative stroke, post-operative myocardial infarction, other post-operative embolic or thrombotic event, and new post-operative dialysis and relative date;

Post-operative serum creatinine level;

Time to recover renal function baseline value, if available;

Any post-operative use of an aminoglycoside antibiotic;

The occurrence of multisystem failure;

Post-operative blood loss;

Status at discharge and if dead the primary cause of death before discharge;

Date of discharge (and post-operative stay).

Note: the average time-to-events for the abovementioned post-operative events are considered the following: less than one day for reoperation for bleeding (Karthik 2004), one day for renal failure (Rosner 2006), 3 days for stroke (Schwann 2007, Hogue 1999, Dafer 2006), 3 days for myocardial infarction (Thygesen 2007), and 6 days for deep vein thrombosis (Hogue 2006). All abovementioned post-operative events have to be collected at any time, even if those occur after the average time-to-events as published in the literature.

The non-key pages are the following:

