1.1.2	End of data collection ²				
1.1.3	Progress report(s)				
1.1.4	Interim report(s)				
1.1.5	Registration in the EU PAS Register®				
1.1.6	Final report of study results.				

¹ Date from which information on the first study is first recorded in the study dataset or, in the case of secondary use of data, the date from which data extraction starts.

² Date from which the analytical dataset is completely available.

Comments:

--

Section 2: Research question	Yes	No	N/A	Section Number
2.1 Does the formulation of the research question and objectives clearly explain:				
2.1.1 Why the study is conducted? (e.g. to address an important public health concern, a risk identified in the risk management plan, an emerging safety issue)				7
2.1.2 The objective(s) of the study?				8
2.1.3 The target population? (i.e. population or subgroup to whom the study results are intended to be generalised)				9.2
2.1.4 Which hypothesis(-es) is (are) to be tested?				
2.1.5 If applicable, that there is no a priori hypothesis?				

Comments:

--

Section 3: Study design	Yes	No	N/A	Section Number
3.1 Is the study design described? (e.g. cohort, case-control, cross-sectional, other design)				9.1
3.2 Does the protocol specify whether the study is based on primary, secondary or combined data collection?				9.3

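### End of data collection is set at the last inclusion, leaving no window for the last patients to reach discharge

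*Protocol*

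**What the plan says.** The planned milestones in the abstract (section 4) give recruitment and data collection the same end point:

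- "Recruitment completed: when a maximum of 5,268 patients will be included (estimated in January 2020"
- "Last data collection: when a maximum of 5,268 patients will be included (estimated in January 2020"

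The milestone table in section 6 uses that trigger for end of data collection: "when a maximum of 5,268 patients will be included (estimated in January 2020".

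The final-report clock starts from two differently named events. Section 6 says the report "will be made available twelve months after the last patient included". The abstract says "Final study report: 12 months after the end of Data collection (prospective collection". Section 12.1 counts 12 months from completion of the study.

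Other parts of the protocol look beyond inclusion:

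- Section 9.3.7 (Key Data) includes "Status at discharge and if dead the primary cause of death before discharge". It also says of post-operative events: "All abovementioned post-operative events have to be collected at any time", even when they come later than the published average times.
- Section 9.7 places the analyses after completion of the Key Data. It also says that patients lacking the needed information are removed rather than imputed.
- Annex 3 (updated ENCePP checklist, footnote 2 to the milestones section) defines end of data collection as "Date from which the analytical dataset is completely available".

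**The concern.** Exposure to aprotinin happens at the operation, which I take as the moment of inclusion. Discharge status, cause of in-hospital death and late complications are known only days or weeks afterwards. If collection ends when the last patient is included, those still in hospital on that day have no final status.

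Who is unfinished is not random. At any fixed date the patients in hospital are a length-biased sample, and a long stay after cardiac surgery is plausibly linked to complications. Removing patients with no recorded status would then take out more of the bad outcomes than of the good ones. In-hospital death is a primary safety measure, so the error would fall on the reassuring side.

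There is also a plain inconsistency of dates. The 12-month report limit has different starting points, which coincide only if data collection really does stop at the last inclusion.

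**Working it through.** **1. The plan's own figures.** Precision for one proportion: n = z² × p(1 − p) / d², with z = 1.96, p = 0.5 and d = 0.0156 (section 9.5). This gives 0.9604 / 0.00024336 = 3,947 after rounding up, against 3,951 stated; 3,951 gives a margin of 1.559%. Inflation for 25% exclusions: 3,951 / 0.75 = 5,268. Both figures reproduce. The exclusions listed in 9.5 are refusal, non-exposure and off-pump surgery, so being analysable does not imply that the outcome record is complete.

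**2. Accrual.** Section 6 gives a start in February 2016 (I use 1 February). The reasons column of the change table in section 5 reports 3,951 analysable patients at the 7 January 2020 extraction. That is 1,436 days, so 3,951 / 1,436 = 2.75 analysable patients per day on average.

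**3. Patients in hospital at the cut-off.** Number = daily accrual × mean post-operative stay. The documents give no length of stay, so the stays below are assumptions.

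| Assumed mean stay | In hospital at cut-off | Share of 3,951 |
|---|---|---|
| 7 days | 19 | 0.5% |
| 10 days | 28 | 0.7% |
| 14 days | 39 | 1.0% |
| 21 days | 58 | 1.5% |

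If accrual at the end ran at twice the average (also an assumption), the range is 39 to 116 patients, or 1.0% to 2.9%.

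**4. Who they are.** Share of long stayers among those in hospital = π × L(long) / [π × L(long) + (1 − π) × L(short)], where π is the proportion of long stayers among all patients. The mixes are assumed:

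- 10% stay 30 days, 90% stay 8 days: 3.0 / 10.2 = 29%.
- 20% stay 30 days, 80% stay 8 days: 6.0 / 12.4 = 48%.
- 5% stay 40 days, 95% stay 8 days: 2.0 / 9.6 = 21%.

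Long stayers are over-represented in each mix, but are not a majority in any of them.

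**5. Effect on in-hospital mortality.** Assume a true rate of 5% (197.55 deaths in 3,951) and a mortality q of 10% to 30% among the k patients in hospital at cut-off, with those deaths not captured.

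- If the k patients are removed: (197.55 − qk) / (3,951 − k). With k = 19 and q = 0.1 this is 4.98%; with k = 58 and q = 0.3 it is 4.63%.
- If they are counted as alive: (197.55 − qk) / 3,951. The same corners give 4.95% and 4.56%.

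The shift is 0.02 to 0.44 percentage points downward. The half-width of the 95% interval at 5% is 1.96 × √(0.05 × 0.95 / 3,951) = 0.68 points.

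**6. The passages side by side.** Three statements need time after the last inclusion: discharge-based Key Data (9.3.7), analysis after completion of Key Data (9.7), and a fully available dataset (Annex 3). Two statements allow none: the section 6 milestone and the last-data-collection line in the abstract.

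**The case against.** The strongest reply is that no sentence closes the record of an included patient. The 5,268 cap may only fix who belongs to the study, with records completed afterwards. Section 9.3 makes Key Data the minimum for every patient, section 9.6 has incomplete records flagged and sites encouraged to complete them, and 12 months are allowed before the final report. On that reading the checklist definition fits and nothing is lost. This stands in part: the documents do not say that outcomes are discarded, and the loss follows only from a literal reading. But the harmless reading needs a completion date or window, and the protocol gives none, while naming the last inclusion as the end of data collection in two places.

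A reader might infer more, in four ways that the documents do not support.

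- **That these patients simply lose their outcomes.** Section 9.8.1 asks for entries close to treatment, and the average times to event quoted in 9.3.7 run from under one day to six days. Many strokes, infarctions and dialysis starts would already be entered, and an entered event is kept.
- **That all thromboembolic and renal incidences are biased downward.** If recorded events stay in and event-free patients without discharge data are removed, those incidences could even rise. The downward direction is clear only for late in-hospital death and late-onset events.
- **That those affected are mainly long-stay complicated cases.** Step 4 shows over-representation, not a majority.
- **That six-monthly interim tables are seriously distorted.** The registry is cumulative, so a record unfinished at one extraction can be complete at the next. That is mostly delay, and interim denominators belong to the statistical analysis plan, which is not shown here.

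**Conclusion.** The point holds as an inconsistency in the protocol with a small, outcome-related consequence. End of data collection coincides with the last inclusion, while the main safety outcomes and the checklist definition need follow-up to discharge. Read literally together with the removal rule, about 19 to 58 of 3,951 patients (0.5% to 1.5%) may lack discharge status. In-hospital death and late-onset events may be slightly understated, by less than the half-width of the confidence interval in the scenarios at average accrual.

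The size rests on assumed stays of 7 to 21 days, average accrual, and assumed mortality rates, none of which the documents supply. The contradiction between the sections rests on no assumption. The final estimates are not seriously threatened. The case for acting is that the loss is avoidable, would err towards reassurance for death, and costs almost nothing to remove.

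**What to change.** - In section 6 and in the abstract, separate the two milestones. Recruitment ends at the 5,268th inclusion. Data collection ends at discharge or in-hospital death of the last included patient, with Key Data completed.
- Start the 12-month final-report clock from that second date in both places, and align section 12.1 with it.
- Version 2.1 is dated March 2020, after the estimated January 2020 trigger. The text should therefore also state the date up to which outcome data were actually accepted.

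The cost is a wording change and a shift of a few weeks in the lock date.

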8.1. Aim of the Study

The aim of the Registry is to collect information over time on the pattern of use of Nordic Aprotinin and to record the proportion of patients exposed to aprotinin in accordance with the authorized indication in participating European countries during the three year period beginning from the day that Nordic Aprotinin becomes available to the market. To have access to Nordic Aprotinin and to become a participating centre, centres have to perform cardiac surgery on cardio-pulmonary bypass and to commit to enrol in the Registry (as described in Annex 4). Thus, it is expected that virtually all patients who receive Nordic Aprotinin at all participating cardiac surgery centre in participating countries in Europe will be included in the Registry. The Registry will provide information on the number of patients who receive Nordic Aprotinin by centre, the recorded indication (surgical procedure, features of the indication), the characteristics, including risk factors and the conditions of use, including adherence to instructions for administration in the approved SmPC. The Registry will also collect additional information from healthcare professionals relevant to patient characteristics that may be related to the decision to use Nordic Aprotinin. Information from the proposed Registry will provide a profile over time of Nordic Aprotinin utilization in participating countries following return to the market.

It is proposed to collect similar information on any patients who are given Nordic Aprotinin within or outside its licensed indications, to allow the assessment of off-label use as part of the missing information, as required in the CHMP assessment report (EMA/590581/2013). **Data collection**

regarding off-label use will be done in accordance with national legal frameworks and will be discussed with the national competent authority prior to launch if necessary and adapted accordingly.

The proposed Registry is expected to be a valuable and informative risk-management tool within the comprehensive EU Risk Management Plan. It is not intended to provide a quantitative assessment of the benefit-risk of treatment with Nordic Aprotinin. The Registry will address specific issues found in the BART study. In that study it was found that some centres were not applying the appropriate safety measures concerning monitoring of blood coagulation. It was also found that some surgical centres had high morbidity and mortality rates. However there were insufficient data available from the BART study to allow analysis of the contribution of these factors (that is the lack of appropriate risk minimisation measures) to an increased risk of morbidity and mortality. This is why this Registry collects information on the monitoring of blood coagulation.

8.2. Primary objectives

The primary objectives of the Registry are to:

1. Monitor the pattern of use and record utilisation information:
 - the proportion of patients exposed to aprotinin in accordance with the authorized indication
2. Measure the incidence of the following adverse events:
 - death and the distribution of the primary cause of death
 - thromboembolic events; the total and individual incidence of myocardial infarction, stroke and other thromboembolic events recorded
 - incidence of renal dysfunction defined as a rise in creatinine from pre-operative to post-operative levels of > 0.5 mg/L, and the incidence of renal dialysis
 - the numbers having an anaphylactic response to aprotinin
3. Measure the effectiveness of risk minimisation measures as described in the RMP and close monitoring of adherence to the SmPC recommendations:
 - the proportion of patients receiving heparinisation monitoring as recommended in the SmPC
 - Proportion of patients with a minimal ACT-celite below 750 seconds
 - Proportion of patients with a minimal ACT-kaolin below 480 seconds
 - the proportion of patients with a post-operative renal dysfunction defined as a rise in creatinine from pre-operative to post-operative levels of > 0.5 mg/L or requiring dialysis known to have received aminoglycoside antibiotics
 - the proportion of patients exposed to aprotinin without the use of test dose (or antibody test)
 - the proportion of patients administered with the recommended posology
 - the proportion of patients administered with less than 2.5 million KIU
 - the proportion of patients administered with more than 7 million KIU

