	
○ thromboembolic events; the total and individual incidence of myocardial infarction, stroke and other thromboembolic events recorded○ incidence of renal dysfunction defined as a rise in creatinine from pre-operative to post-operative levels of > 0.5 mg/L, and the incidence of renal dialysis○ the numbers having an anaphylactic response to aprotinin 
3. Measure the effectiveness of risk minimisation measures as described in the RMP and close monitoring of adherence to the SmPC recommendations:
 
○ the proportion of patients receiving heparinisation monitoring as recommended in the SmPC○ the proportion of patients with a post-operative renal dysfunction defined as a rise in creatinine from pre-operative to post-operative levels of > 0.5 mg/L or requiring dialysis known to have received aminoglycoside antibiotics○ the proportion of patients exposed to aprotinin without the use of test dose (or antibody test)○ the proportion of patients administered with the recommended posology 
The secondary objectives of the Registry are to:
 
1. Estimate the contribution of suspected risk factors to adverse events:
○ the proportion of patients with total and individual thrombotic events who did not receive heparinisation monitoring as recommended in the SmPC (regarding the risks related to heparinisation monitoring)○ the proportion of patients with anaphylactic reactions who had previously been exposed to aprotinin (solution or fibrin sealant containing aprotinin) in the last 12 months2. Estimate information concerning:
○ the proportion of pregnant and lactating women○ the proportion of patients undergoing repeat isolated CABG○ the proportion of patients having a concomitant use of drugs that affect haemostasis (including antiplatelet therapy) and/or non-VKA oral anticoagulant considered as active at time of surgery and relating safety outcomes when aprotinin is used in those patients○ the proportion of patients over 75 years of age and outcomes: the proportion of these patients requiring re-operation for bleeding; the mortality rate
--	--

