9.3.1. Initial Registry data *

Age;
Gender;
Centre;
Anaesthetist;
Country;
Date of surgery;
Date of admission;
Procedure group;
Use of cardiopulmonary bypass;
Renal impairment;
Last pre-operative creatinine;
Pregnancy;
Lactation;

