9.5. Study size

All patients exposed to Nordic Aprotinin, at all participating cardiac surgical centres in European countries with marketing authorisation, are intended to be included during the study.

The study is designed primarily to monitor the pattern of use and record utilisation information such as the proportion of patients exposed to aprotinin in accordance with the authorized indication.

Considering that the registry of Great Britain & Ireland recorded just over 400,000 operations in 5 years and that the US one collected around 280,000 operations/year^{15,16}, we could postulate that, across Europe, at least 300,000 patients are undergoing cardiac surgery.

Thus, we estimate the sample size based on the occurrence of events of specific interest (such as type of procedure, death, thromboembolic, stroke ...) with a reasonable precision.

To obtain 95% confidence interval with a maximum margin error of 1.56%, 3,951 patients should be included. This margin error is the maximum one that can be obtained: it is the one based on the assumption that an event of interest is observed in 50% of patients (meaning a 95% CI of [48.44% ; 51.56%]). In all other cases (i.e. event of interest observed in less or more than 50%), precision will only be better (less than 1.56%).

There is no a priori calculation of power for this study because the main primary objective is descriptive rather than inferential and because the adverse event included in the other primary objectives such as in-hospital mortality, thromboembolic events or renal dysfunction are dependant of aprotinin's pattern of use.

Taking into account an exclusion rate of 25% (patient refusing data collection, un-exposed to aprotinin in the course of cardiac surgery with CPB, or undergoing off pump surgery), the number of patients to include is 5,268.

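### Renal dysfunction is defined by a creatinine rise of > 0.5 mg/L (0.05 mg/dL), an unexplained and very small cut that is probably a unit slip and would count measurement variation as cases

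*Protocol*

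**What the plan says.** Section 8.2 uses the threshold twice. Primary objective 2 measures the "incidence of renal dysfunction defined as a rise in creatinine from pre-operative to post-operative levels of > 0.5 mg/L", with the incidence of dialysis as a companion measure in the same bullet. Primary objective 3 takes patients with "post-operative renal dysfunction defined as a rise in creatinine from pre-operative to post-operative levels of > 0.5 mg/L or requiring dialysis" and asks what proportion are known to have received aminoglycosides.

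The abstract (section 4) repeats both: "incidence of renal dysfunction defined as a rise in creatinine from pre-operative to post-operative levels of > 0.5 mg/L, and the incidence of renal dialysis" under objective 2, and "the proportion of patients with a post-operative renal dysfunction defined as a rise in creatinine from pre-operative to post-operative levels of > 0.5 mg/L" under objective 3. All four statements are current text and all four give mg/L.

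The two values needed to compute the rise are Key Data: "Last pre-operative creatinine" in section 9.3.1 and "Post-operative serum creatinine level" in section 9.3.7. Neither entry names a unit. Nowhere does the protocol restate the threshold in mg/dL or µmol/L, cite a source for it, or explain its size.

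**The concern.** A rise of 0.5 mg/L is about 4 to 6% of a baseline between 8 and 12 mg/L (an assumed range; the protocol gives no creatinine distribution). A change of that size can arise from assay and day-to-day variation alone, so the definition does not separate renal dysfunction from no change.

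Two results rest on it. The first is a primary-objective incidence for renal impairment, which Table 1 in section 8.3 lists as an important identified risk. The second is the case group for the aminoglycoside measure, which addresses an interaction listed in the same table. False cases raise the first. In the second they pull the observed aminoglycoside share towards that of patients without renal injury, so a real interaction would be harder to see. Section 9.7 also plans to use external cardiac surgery databases as a yardstick, and a rate built on this cut is comparable only with a source that uses the same one.

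**Working it through.** **What can be reproduced.** The threshold is a definition without a derivation, so there is no figure of the plan's to reproduce for it. The sample size can be checked, to see whether it depends on the threshold. Section 9.5 states: "To obtain 95% confidence interval with a maximum margin error of 1.56%, 3,951 patients should be included".

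- n = 1.96² × 0.25 / 0.0156² ≈ 3,947; conversely, the margin at n = 3,951 and p = 0.5 is 1.559%.
- 3,951 / 0.75 = 5,268.

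Both figures stand, and neither uses the creatinine cut.

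**Unit conversion.**

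- 0.5 mg/L ÷ 10 = 0.05 mg/dL.
- 0.5 mg/L ÷ 113.12 g/mol × 1000 = 4.42 µmol/L.
- Ten times larger: 5 mg/L = 0.5 mg/dL = 44.2 µmol/L.

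**How often variation alone crosses the cut.** Inputs from the protocol: threshold 0.5 mg/L, and one pre-operative and one post-operative value. Inputs assumed: baseline 8, 10 or 12 mg/L; total within-patient CV 2 to 10%; normal errors, independent between the two measurements; no true change.

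The difference of the two values then has mean 0 and SD = √2 × CV × baseline, and

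P(rise > c) = 1 − Φ(c / SD).

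Worked case, baseline 10 mg/L and CV 5%: SD = 1.414 × 0.05 × 10 = 0.707 mg/L; 0.5 / 0.707 = 0.707; P = 24.0%.

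Share of patients with no true change whose rise exceeds 0.5 mg/L:

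| Baseline (mg/L) | CV 2% | CV 3% | CV 5% | CV 8% | CV 10% |
|---|---|---|---|---|---|
| 8 | 1.4% | 7.0% | 18.8% | 29.0% | 32.9% |
| 10 | 3.9% | 11.9% | 24.0% | 32.9% | 36.2% |
| 12 | 7.0% | 16.3% | 27.8% | 35.6% | 38.4% |

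With a cut of 5 mg/L the worst cell (12 mg/L, CV 10%) has SD = 1.697 mg/L, 5 / 1.697 = 2.946 and P = 0.16%. At 10 mg/L and CV 10% it is 0.02%.

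**Effect on the two measures.** Let q be the share of patients with no true change and f the table entry.

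- False cases add q × f to the renal incidence. The protocol gives no value for q, so f is the addition only in the limiting case q = 1.
- With T true and F false cases, whose aminoglycoside shares are a_T and a_F, the observed share is (T·a_T + F·a_F) / (T + F). It moves towards a_F as F grows.

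**The case against.** **The unit is consistent, so it may be intended.** A reader might infer that a ten-fold unit error is proven. It is not: all four statements agree, the protocol does not contradict itself, and nothing in it shows mg/dL. What can be shown is that the printed cut is very small and has no stated rationale. Consistency does not supply one, so the threshold needs either correction or justification.

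**The SAP or eCRF may hold the right unit.** The SAP is listed as Annex 6, but its text is not in the document. The programmed cut and the unit of storage are normally fixed there, and their absence from the protocol is no fault. The point here is different: a value is stated, and it looks wrong. If the SAP uses another cut, it disagrees with the protocol's own primary-objective definition, and section 12.3 commits to reporting in strict accordance with both.

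**The effect may be small.** This stands in part. At CV 2% and baseline 8 mg/L only 1.4% of unchanged patients cross the cut. Elsewhere on the grid the share is larger, and from CV 5% upwards it is never below 18.8%.

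**Much of the renal assessment does not use the cut.** This stands. Dialysis incidence is measured separately, dialysis is also a route into the aminoglycoside group, and the renal failure outcomes in section 9.7 are not defined by this threshold. The study's main objective, use within the authorised indication, is untouched.

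**Conclusion.** The definition should not go into the final analysis as it stands. The conversion to 0.05 mg/dL (4.4 µmol/L) is certain. That mg/dL was meant is probable, but it is an inference. The false-positive share of 1.4% to 38.4% (24% at 10 mg/L and CV 5%) rests on assumed baselines and CVs and applies only to patients with no true change. At a cut ten times larger it is at most about 0.2%.

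Three stronger readings are tempting and should not be adopted:

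- *That the renal incidence would be mostly noise.* This needs the share of patients with a true post-operative rise, which the protocol does not give.
- *That 947 false cases are to be expected (24.0% of 3,951).* This holds only if no patient's creatinine truly changes, so it describes a hypothetical cohort.
- *That no external comparison is possible.* Both creatinine values are collected, so another cut can be applied at analysis. The harm is a misleading reported rate, and no information is lost.

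**What to change.** 1. Confirm with the sponsor which unit was intended.
2. Correct the threshold in all four places (abstract, objectives 2 and 3; section 8.2, objectives 2 and 3). If 0.5 mg/dL is meant, write > 0.5 mg/dL (5 mg/L; 44 µmol/L). If mg/L is intended, keep it and add a justification for a cut of that size.
3. Check that the analysis program applies the threshold in the same unit as the stored creatinine values, with any conversion stated.
4. If any renal table has been produced with the mg/L cut, re-run it together with the aminoglycoside table.

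The cost is a one-line text correction in four places, a programming check and possibly a re-run. No new data are needed, and the sample size does not change.
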